9.3.1 Variables for Cystic Fibrosis Trust Patient Registry (UK)

9.3.1.1 Exposure

Ivacaftor exposure will be determined by first evidence of ivacaftor treatment and patients will remain exposed until there is evidence of discontinuation of ivacaftor in the patient registry database. Because start and stop dates are available, ivacaftor exposure will be calculated in days. When start and stop dates are not available due to missing data, algorithms will be used to extrapolate duration of exposure based on timing of patient encounters and drug exposure data available. The exposure algorithm includes the following rules: if only month and year are available, then the assumed start or stop date will be the 15th of the month, or if only year is available, then the assumed start or stop date will be June 30th. Ivacaftor exposure will be categorised into the meaningful groups based on the distribution of exposure, such as <1 year, 1 to <2 years, and ≥2 years. For patients who discontinue treatment with ivacaftor, reason for discontinuation (lack of benefit, side effect, other) will be described.

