16.2 Drug Utilisation Subprotocol

The drug utilisation subprotocol will be conducted using the same Drug Utilisation Cohort definition (Section 9.1.2.6), analysis variables (Section 9.3.2.3), and statistical analysis (Section 9.3.4.3), as specified in the main protocol for Objective 3 (drug utilisation).

To meet the subprotocol objective, data for outcomes will be analysed separately for each registry starting at Year 2 of the main protocol. All enrolled patients exposed to ivacaftor will be included in the Drug Utilisation Cohort. Ivacaftor exposure will be derived as described for the CF Trust (Section 9.3.1.1) if start and stop dates of ivacaftor treatment are available, or as described for the CF Foundation (Section 9.3.2.1) if start and stop dates of ivacaftor treatment are not available.

Drug utilisation of ivacaftor will be described by the frequency of ivacaftor exposure, by *CFTR* genotype class, age, sex, and percent predicted FEV₁. Because ivacaftor was not available in Ireland and France until 2013, data for drug utilisation analyses will not be available for Vertex until 2014; therefore, data will be analysed separately for each registry for 4 years. The milestones for the annual reports are provided in Table 8.

Table 8 Subprotocol Study Milestones

Milestone ^a	Planned Dates	
	Ireland	France
Start of data collection ^b	May 2014 ^c	May 2014 ^c
End of data collection ^b	May 2017	May 2017
Year 1 Report	not applicable	not applicable
Year 2 Report	October 2014	October 2014
Year 3 Report	October 2015	October 2015
Year 4 Report	October 2016	October 2016
Registration in EU PAS Register ^d	tbd	tbd
Final report of study results	October 2017	October 2017

CF: cystic fibrosis; EU PAS: European Union Post-authorisation Study; tbd: to be determined.

^a Milestones are based on the main protocol (i.e., the Year 1 Report is relative to the start of data collection for the CF Trust [UK] and CF Foundation [US] registries).

^b Per EU Good Pharmacovigilance Practices VIII.B.2, the start and end of data collection for secondary use of data are when the analytical datasets are available.

^c Because ivacaftor was not commercially available until 2013, data for drug utilisation analyses will not be available for extraction until 2014. Therefore, subprotocol reports will begin with the Year 2 (relative to the main protocol).

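### As written, the UK partial-date rule can give zero or negative days of exposure, a stop after death, or a start later than an encounter already recording ivacaftor

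*Protocol*

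**What the plan says.** Protocol section 9.3.1.1 states that UK exposure is measured in days from recorded dates: "Because start and stop dates are available, ivacaftor exposure will be calculated in days". Exposure runs from the first evidence of treatment, and "patients will remain exposed until there is evidence of discontinuation of ivacaftor in the patient registry database". Death is not named as an end of exposure.

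For missing dates, "algorithms will be used to extrapolate duration of exposure based on timing of patient encounters and drug exposure data available". The section then says "The exposure algorithm includes the following rules" and gives two:

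- "if only month and year are available, then the assumed start or stop date will be the 15th of the month";
- "if only year is available, then the assumed start or stop date will be June 30th".

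Duration is then grouped into bands, "such as <1 year, 1 to <2 years, and ≥2 years". It stratifies all six safety outcomes (9.3.4.1) and the disease-progression analyses (9.3.4.4), and it is used to describe pregnancies (9.3.4.2). The start date also fixes the UK baseline FEV₁, which section 9.3.1.3 defines as the latest value before ivacaftor was begun. That registry holds one lung function measure per patient per calendar year.

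**The concern.** The same mid-period date is assigned whether the missing item is a start or a stop, and neither rule looks at anything else known about the patient. Three impossible or misleading results can follow:

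- a stop on or before the start;
- a stop after death;
- a start later than an encounter at which ivacaftor was already recorded.

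Zero and negative durations arise only in courses that begin and end within one calendar year or month, and among those the shortest are hit most often. The UK registry is the one with stop dates and stop reasons (Table 4), and section 8.3 rests its hypothesis on adverse events leading to withdrawal on UK data alone. Short UK courses are therefore of particular interest. The registries run the analyses and the sponsor receives only final tables (9.6), so the sponsor could not see a negative duration in the records.

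The US rule in section 9.3.2.1 avoids the ordering problem by construction. It takes the first encounter showing exposure as the start and a later encounter without it as the stop.

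**Working it through.** The protocol states no figure that depends on this rule, so there is none to reproduce. The inputs are the two anchors in 9.3.1.1. The formula is duration = imputed stop minus imputed start, in days.

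**Individual cases**

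| Start | Stop | Result |
|---|---|---|
| 2013 (year only) | 2013 (year only) | 30 June - 30 June = 0 days |
| March 2013 (month only) | March 2013 (month only) | 15 March - 15 March = 0 days |
| 10 October 2013 | 2013 (year only) | 30 June - 10 October = -102 days |
| 2013 (year only) | 1 April 2013 | 1 April - 30 June = -90 days |
| 2013 (year only) | March 2013 (month only) | 15 March - 30 June = -107 days |
| 20 March 2013 | March 2013 (month only) | 15 March - 20 March = -5 days |

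The extremes are -184 days (start 31 December, year-only stop) and -180 days (year-only start, stop 1 January).

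**How often, given a same-year course with exactly one year-only date.** Assume every ordered pair of days in a 365-day year is equally likely. 30 June is day 181, leaving 184 later days.

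- Year-only stop: the duration is negative when the start is after 30 June, so both dates are. Probability ≈ (184/365)² = 0.254. An exact count of day pairs gives 0.253 negative plus 0.003 zero.
- Year-only start: the duration is zero or negative when the stop is on or before 30 June. Probability ≈ (181/365)² = 0.246. The exact count gives 0.243 negative plus 0.003 zero.

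By true length of course, the share giving zero or fewer days is:

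| True duration | Year-only stop | Year-only start |
|---|---|---|
| 14 days | 48.7% | 47.6% |
| 30 days | 46.3% | 45.1% |
| 90 days | 34.5% | 33.1% |
| 180 days | 2.7% | 0.5% |

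For example, a 30-day course has 365 - 30 = 335 possible start days, of which 155 fall on or after 30 June: 155/335 = 46.3%.

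**Where the sign cannot go wrong.** If the two dates lie in different calendar years, the smallest result is 181 days with a year-only stop (31 December to 30 June), 185 days with a year-only start (30 June to 1 January) and 365 days with both. Complete dates are unaffected.

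**Stop after death.** Take a start of 1 May 2013, death on 1 March 2014 and a year-only 2014 stop.

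- Imputed duration: 1 May 2013 to 30 June 2014 = 365 + 60 = 425 days.
- Longest possible true duration: 1 May 2013 to 1 March 2014 = 304 days.
- The stop is placed 425 - 304 = 121 days after death. The maximum, for a death on 1 January, is 180 days.

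This patient belongs under 1 year but is placed in the 1 to <2 years band.

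**Baseline FEV₁.** Suppose treatment truly began in February 2013, the start is recorded only as 2013, and an April 2013 encounter records both ivacaftor and the year's FEV₁. The imputed start is 30 June. The latest earlier FEV₁ is then the April value, taken on treatment. The true baseline would be an earlier year's value.

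**The case against.** The strongest reply is that these are two listed components of a wider algorithm. The section says it includes them, refers to encounter timing, and leaves detail to an SAP that is not shown. Checks that a stop follows a start, and caps at death, are ordinary SAP content, and section 9.6.1 describes monthly verification and site queries. Part of this stands: the absence of such checks alone would not be a fault in a protocol. But the protocol did not defer date imputation. It prescribed specific dates, and a general mention of encounters does not say that those dates give way when they conflict with what is known.

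A reader might infer several stronger things that the documents do not support.

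- *Early discontinuers drop out of the Ivacaftor Cohort.* Entry needs only evidence of treatment (9.1.2.1, 9.2.6, 9.3.1.1). No positive duration is required.
- *Zero or negative values put patients in the wrong stratum.* A same-year course belongs under 1 year, and 0 or -102 days also falls there. The stratum error arises from the stop after death.
- *The account of discontinuation is corrupted.* The reason for stopping is a recorded field and does not depend on duration.
- *Early discontinuers in general get zero or negative days.* This needs a partial date and a course within one year (or one month). Even then it is certain only when both dates fall on the same anchor.
- *The error passes to Ireland and France.* Section 16.2 says "Ivacaftor exposure will be derived as described for the CF Trust (Section 9.3.1.1) if start and stop dates of ivacaftor treatment are available", and otherwise uses the US rule. Those analyses report frequency of exposure by genotype class, age, sex and FEV₁, not duration.

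The uniform assumption is also open to challenge. Section 6 dates UK reimbursed supply from January 2013. If starts clustered early in that year, the failure rate for a known start with a year-only stop would be below 25%.

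**Conclusion.** The point holds in limited form. The prescribed UK anchors can produce impossible values, and no text in the protocol prevents it. The effects that can be shown are:

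- wrong days of exposure, including zero and negative values, for same-year or same-month courses with a partial date;
- a possible shift across the 1-year band when a year-only stop falls after death;
- a possible on-treatment value serving as baseline FEV₁ when a start is imputed too late.

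The 25% figure is conditional on a same-year course with exactly one year-only date, and it rests on equally likely date pairs. The overall number of patients affected cannot be computed, because the rate of partial UK dates is not stated, and it could be small. Cohort membership, the reason for discontinuation and the prior-exposure flag (start before January 2013, which needs only the year) are unaffected. The change is worth making because the rule is explicit and the correction is cheap, not because a large bias has been shown.

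**What to change.** In section 9.3.1.1, and correspondingly in the SAP, keep the 15th and 30 June only where they agree with every known date for the patient. Otherwise impute the midpoint of the admissible interval within the recorded month or year, bounded as follows:

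- **Start:** no later than the known stop, the first encounter recording ivacaftor, or death.
- **Stop:** no earlier than the start or the last encounter recording ivacaftor, and no later than the first encounter recording that it was stopped, death, or data lock.
- **Ordering:** require the stop to be on or after the start.
- **Both dates partial in the same period:** flag duration as unknown but under 1 year (or under 1 month), rather than entering 0 days.

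If the SAP already contains these bounds, a cross-reference in 9.3.1.1 is enough.

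The cost is one paragraph and some extra programming. Death and encounter data are already in the registry, so nothing new is collected. One limit is that the UK registry holds annual data for each patient (section 4), so the encounter bounds may often be wide and the imputed date correspondingly imprecise.

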9.3.1.2 Outcomes

Death will be defined if there is evidence of a date of death in the database. Cause of death will include respiratory/cardiorespiratory, liver disease, trauma, suicide, transplant-related, and other.

Organ transplantations will be defined if there is evidence of an organ transplantation. Type of transplant will include lung and other.

Hospitalisations will be defined if there is evidence of a start date for a hospitalisation for a pulmonary exacerbation.

CF complications include the following:

- allergic bronchial pulmonary aspergillosis (ABPA)
- absence of vas deferens
- arthritis
- arthropathy
- asthma
- bone fracture
- cancer confirmed by histology
- cardiac disease
- CFRD
- chronic *P aeruginosa* colonisation
- chronic *Staphylococcus aureus* colonisation
- cirrhosis with portal hypertension
- cirrhosis with no portal hypertension
- depression
- DIOS
- fibrosing colonopathy/colonic stricture
- gallbladder disease requiring surgery
- gastroesophageal reflux disease (GERD)
- gastrointestinal (GI) bleed (non-variceal) requiring hospitalisation
- GI bleed (variceal) requiring hospitalisation
- Haemoptysis
- Hearing loss
- hypertension
- kidney stones
- liver disease, non-cirrhosis
- liver enzymes elevated
- nasal polyps requiring surgery
- nontuberculous mycobacteria (NTM) infection (not requiring treatment)
- NTM infection (requiring treatment)
- osteopenia
- osteoporosis
- pancreatitis
- peptic ulcer disease
- pneumothorax requiring chest tube
- port inserted or replaced
- rectal prolapse
- renal failure requiring dialysis
- septicaemia
- sinus disease
- other, specify including cataract

Pulmonary exacerbations will be defined by evidence of a CF care episode or hospitalisation with reason pulmonary exacerbation. Respiratory microbiology will include patients with a bacterial culture and evidence of chronic colonisation with *Staphylococcus aureus*, chronic *P aeruginosa*, intermittent *P aeruginosa*, *Burkholderia*, methicillin-resistant *Staphylococcus aureus*, and *Haemophilus influenzae*.

Serious safety outcomes will be defined by combining death, organ transplantations, hospitalisations, and selected CF complications.

Pregnancy will be defined if there is evidence of pregnancy in the database. Pregnancy data are collected for female patients 13 years of age and older. Outcomes include live birth, stillbirth, spontaneous abortion, therapeutic abortion, undelivered, and unknown. In addition, gestational age and congenital anomalies will be included.

Cardiac disease will be defined by specification of cardiac disease as a CF complication.

CF lung disease severity will be defined if there is evidence of pulmonary function test results in the database. Absolute measures (in litres) for FEV₁ (best FEV₁ during last period) are collected. Percent predicted FEV₁ will be calculated based on the Hankinson³⁰ or Wang³¹ equations (see Section 9.3.4.4).

Clinical signs of CF disease progression will be defined by outcomes previously specified, including death, organ transplantation, and selected CF complications (CFRD and DIOS).

Change in lung function over time will be defined by pulmonary function test results over the years in the analysis. Absolute measures (in litres) for FEV₁, forced vital capacity (FVC) and forced midexpiratory flow (FEF_{25%-75%}) (best values during last period) are collected. Percent predicted values will be calculated based on the equations of Hankinson et al.³⁰ or Wang et al.³¹ (see Section 9.3.4.4).

9.3.2 Variables for Cystic Fibrosis Foundation Patient Registry (US)

9.3.2.1 Exposure

Ivacaftor exposure will be determined by first evidence of ivacaftor treatment and patients will remain exposed until there is evidence of discontinuation of ivacaftor in the patient registry database. Because start and stop dates are not available, algorithms will be used to extrapolate duration of exposure based on timing of patient encounters and drug exposure data available. The exposure algorithm includes the following rules: the date of the first encounter with evidence of ivacaftor exposure will be used as the start date. Patients will be identified as exposed to ivacaftor until a medications form is completed where ivacaftor treatment is not reported. The ivacaftor stop date will be the encounter date where exposure is not indicated. Ivacaftor exposure will be categorised into the meaningful groups based on the distribution of exposure, such as <1 year, 1 to <2 years, and ≥2 years.

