6 MILESTONES

Based on the marketing authorisation dates of ivacaftor in the United States (US; 31 January 2012) and European Union (EU; 23 July 2012), the milestones for data collection and analysis are different for the 2 patient registries, as indicated in the table below. Ivacaftor was first made commercially available in the US in February 2012. Ivacaftor has been commercially available (reimbursed) in the United Kingdom (UK) since January 2013. Each year, the Cystic Fibrosis (CF) Trust and CF Foundation create a data set for the patient registries. The process includes a data lock point of 31 December (US) and 31 January (UK) followed by a 3- to 4-month data entry and data cleaning period when sites are queried for data discrepancies. The final data made available to Vertex by the registries in April/May (US) and June (UK) each year will comprise patient data from the previous calendar year. Vertex's summary of the data provided and the preparation and submission of an annual study report are expected to be a 5- to 6-month process.

The milestones provided are based on protocol finalisation by June 2013.

Table 1 Study Milestones

Milestone	Planned Date	
	CF Trust (UK)	CF Foundation (US)
Start of data collection ^a	June 2013 ^b	June 2013 ^b
End of data collection ^a	June 2017	May 2017
Year 1 Report	December 2013 ^c	December 2013 ^c
Year 2 Report	December 2014	October 2014
Year 3 Report	December 2015	October 2015
Year 4 Report	December 2016	October 2016
Registration in EU PAS Register ^d	tbd	tbd
Final report of study results	December 2017	October 2017

CF: cystic fibrosis; EU PAS: European Union Post-authorisation Study; tbd: to be determined; UK: United Kingdom; US: United States.

^a Per EU Good Pharmacovigilance Practices VIII.B.2, the start and end of data collection for secondary use of data are when the analytical datasets are available.

^b Data for the Historical Cohort will have been collected by the registries before ivacaftor was commercially available in the respective regions. The data extraction for the Historical Cohort will be conducted as part of the Year 1 Report activities.

^c Based on the protocol finalisation date, the Year 1 Report will be completed later in the year than later annual reports (i.e., December instead of October).

^d Study will be registered in EU PAS Register following Pharmacovigilance Risk Assessment Committee approval of final protocol and before study initiation.

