Observational or noninterventional study design is the preferred method used to understand the safety of products in the "real-world" setting and allows for data collection of outcomes without influencing treatment patterns. Once market authorisation is achieved, it is expected that a broader patient population will be exposed to the drug compared to the population exposed in the clinical development programme. The observational design allows for the study of outcomes in the newly exposed population and, because of the availability of historical data for patients enrolled in the registries, previously exposed patients. With this design, we estimate that a subset of patients who were exposed to ivacaftor during clinical development and continue to be treated with ivacaftor will have exposure durations of greater than 5 years when analysed for the annual reports.

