9.2.5 Other Matching Considerations

Given the limited size of the CF population, the Comparator and Comparator Pregnancy Cohorts will not be matched for other measures of disease severity (e.g., percent predicted FEV₁, *Pseudomonas aeruginosa* infection) due to concerns about availability of adequate patients for matching. However, measures of disease severity will be included as stratification variables and as covariates for adjustment, as necessary.

The Historical Cohort will include patients with a *G551D-CFTR* mutation who were in the patient registries in 2008. These patients were chosen because they represent the best match to ivacaftor-treated patients in 2012 and later because they match the indicated patient population based on the approved product labelling. The Historical Cohort will include patients of all ages and will be stratified to identify outcomes for patients younger than 6 years of age (for the potential off-label population). The year 2008 was chosen because starting in 2009, ivacaftor clinical studies were actively enrolling in the UK and US. A 1-year window was selected to match the window for safety outcome analysis in the Ivacaftor and Comparator Cohorts. The Historical Cohort will be analysed once for Objectives 1 and 2 for all stratification variables. If additional analyses are identified during the conduct of the study, the Historical Cohort will be available for analysis.

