9.3 Variables

All variables for study endpoints are collected in prespecified data collection forms. For example, specific diagnoses are captured as data elements rather than as a collection of information from which a diagnosis would be made. Adjudication is done by the governing committees of the patient registries. Investigators (physicians with expertise in CF) from certified CF centres complete the forms according to the data guidelines and indicate the specified diagnoses for patients. Because verbatim terms are not reported and forms contain adjudicated diagnoses, the data are inherently coded. Each registry employs its own data entry guideline rather than use external coding dictionaries.

The CF Trust and CF Foundation patient registries employ data collection instructions and rigorous data cleaning procedures to provide robust data sets for the analysis of ivacaftor safety, drug utilisation, and CF disease progression. The principal investigators of this protocol are both physicians with expertise in CF, familiar with the current standards for treating patients with CF, as well as the data quality process of their respective registries. Therefore, an external expert committee for validation of diagnoses is not planned.

The CF Trust and CF Foundation independently determine the data to be collected; thus, the specific variables included in the analyses for this study are not necessarily identical. Types of variables important for this analysis include exposure, outcomes, and stratification variables. Stratification variables will be explored to identify confounders and effect modifiers. Data are collected for each patient registry; therefore, variables are described separately (Sections 9.3.1 and 9.3.2). Table 4 provides a comparison of the variables to be collected.

Table 4 Comparison of Variables Collected by the Patient Registries

Variables	CF Trust (UK)	CF Foundation (US)
Exposure	start/stop (reason)	yes (150 mg/other)/no
Prior ivacaftor exposure	Derived based on start date before January 2013	Derived based on ivacaftor exposure in 2012
Death	date; cause (respiratory/ cardiorespiratory, liver disease, trauma, suicide, transplant-related, other)	date; cause (respiratory/ cardiorespiratory, liver disease, trauma, suicide, transplant-related, other, unknown)
Organ transplantation	yes (lung, other)/no	yes (lung, liver, kidney, other)/no

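### The US start-date rule drops clinical-study exposure that the registry did not record, so US durations are minimums and cannot show more than 5 years unless ivacaftor was recorded before 2012

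*Protocol*

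**What the plan says.** Protocol 9.3.2.1 explains why the US registry needs a derived duration: "Because start and stop dates are not available, algorithms will be used to extrapolate duration of exposure". The rule that follows is that "the date of the first encounter with evidence of ivacaftor exposure will be used as the start date". Exposure then runs until a medications form no longer shows the drug. Durations are to be grouped into bands "such as <1 year, 1 to <2 years, and ≥2 years", offered as examples to be settled on the observed distribution. No rule adds exposure that preceded the first recorded encounter.

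Protocol 9.1 estimates that a subset of patients "exposed to ivacaftor during clinical development and continue to be treated with ivacaftor will have exposure durations of greater than 5 years" at the annual reports. It names no registry, and it points to historical registry data as the reason previously exposed patients can be studied.

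Four other places bear on this:
- Section 9.2.5: "starting in 2009, ivacaftor clinical studies were actively enrolling in the UK and US".
- Section 6: "Ivacaftor was first made commercially available in the US in February 2012". The US data lock is 31 December each year.
- Table 4: US prior exposure is "Derived based on ivacaftor exposure in 2012", whereas the UK entry relies on a recorded start date before January 2013.
- Section 9.3.5: the length of earlier ivacaftor exposure is to be assessed as a confounder or effect modifier, when possible.

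**The concern.** Duration of exposure stratifies all six safety categories of Objective 1 (9.3.4.1) and the Objective 4 analyses (9.3.4.4). It is also used to describe pregnancies (9.3.4.2). If the US clock starts at the first registry record, a patient treated in a study for two or three years before launch looks the same as a patient who began commercial drug in 2012. The patients who say most about long-term safety are then mixed with recent starters, which blurs both early and late risk.

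The US registry is the larger of the two: 1035 patients with *G551D* against 432 in 9.5. It is also the only source of the Ivacaftor versus Comparator comparison in the Year 1 Report (Table 2).

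The text elsewhere does not repair this. A variable built on exposure in 2012 cannot separate a 2009-2011 study patient from a 2012 commercial starter, so it cannot supply the earlier duration that 9.3.5 wants. Section 9.9 does not list the truncation among the limitations.

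**Working it through.** **Inputs.** Study enrolment from 2009 (9.2.5). US approval 31 January 2012 and launch February 2012 (section 6). Data years 2012 to 2016 (Abstract, Data Analysis). US lock 31 December (section 6). Example bands (9.3.2.1).

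**Formula.** Duration = (lock date − start date in days) / 365.25, for a patient who stays on the drug.

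**Step 1: the plan's own figure, with true start dates.** A start on 1 January 2009 gives 6.00 years at the 2014 lock and 8.00 at the 2016 lock. A start on 31 December 2009 gives 7.00 at the 2016 lock, and 31 December 2010 gives 6.00. The estimate of more than 5 years is therefore attainable when true starts are known.

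**Step 2: the US rule.**

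| First recorded encounter | 2012 lock | 2013 lock | 2014 lock | 2016 lock |
|---|---|---|---|---|
| 31 Dec 2011 | 1.002 | 2.001 | 3.001 | 5.002 |
| 1 Jan 2012 | 0.999 | 1.999 | 2.998 | 4.999 |
| 1 Feb 2012 | 0.914 | 1.914 | 2.913 | 4.914 |
| 1 May 2012 | 0.668 | 1.667 | 2.667 | 4.668 |

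For example, 1 February 2012 to 31 December 2016 is 1795 days, and 1795 / 365.25 = 4.914 years. A first record inside 2012-2016 never gives more than 5 years. A record on 31 December 2011 just does, so the result turns on whether the registry held any ivacaftor entry before 2012.

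**Step 3: exposure lost.** The most is from 1 January 2009 to 1 February 2012: 1126 days, or 3.08 years. A study start late in 2011 loses almost nothing.

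**Step 4: bands.** Take a patient who started in a study in 2009-2011, stayed on the drug, and first appears in the registry in early 2012.
- 2012 data: true 1.0 to 4.0 years, derived at most 1.00. Band: under 1 year.
- 2013 data: true 2.0 to 5.0 years, derived at most 2.00. Band: 1 to under 2 years.
- 2014 data: derived about 2.9 years. Band: 2 years or more, which is also the true band.

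Thus, if no record precedes 2012, the top example band is empty in the US until the 2014 data, whatever the patients' real histories.

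**The case against.** The other side has several fair points.

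- **Section 9.1 may be satisfied elsewhere.** It offers an estimate about a subset and names no registry. UK start dates can carry exposure from before 2013. This stands: the two sections conflict only if the statement is read as covering US data.
- **Earlier US records may exist.** A reader might infer that no US group with more than 5 years can exist. The protocol does not support that. It nowhere says when the US registry began recording ivacaftor; it gives such a date (2013) only for the UK, in a note to Table 2. Section 9.1 appeals to historical registry data, and 9.3.2.1 does not confine the first encounter to 2012-2016. The Table 4 entry suggests a 2012 beginning but does not state it.
- **The exclusion criterion removes some cases.** A patient who went straight from a study to commercial drug in February 2012 was in an interventional study during the 2012 analysis period. Where that is recorded, 9.1.2.1 excludes the patient from the 2012 data. The 2012 misbanding then concerns only patients whose participation was not recorded or had ended before 2012. The exclusion does not help with the 2013 data.
- **The effect fades.** A reader might infer that study patients are treated as new users throughout. Under the example bands this ends with the 2014 data. Objective 4 is not reported in Year 1, and the final report is unaffected unless finer upper bands are used. The bands are only examples.
- **Prior exposure is mentioned.** Table 4 and 9.3.5 show that the issue was seen, but the US definition cannot deliver the duration needed for study exposure.

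What remains is that the start rule is fixed in the protocol, no text adds unrecorded study exposure, and the truncation is not disclosed.

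**Conclusion.** The point holds in a limited form. The US duration variable measures recorded exposure, which is a minimum for former study patients. It can fall short by up to about 3.1 years for a patient first recorded at launch. Unless ivacaftor was recorded in the US registry before 2012, no derived US duration exceeds 5 years (4.91 from 1 February 2012), and the estimate in 9.1 cannot be shown from US data.

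Under the example bands the misclassification affects the 2012 data (for those not excluded) and the 2013 data. It persists later only if the open top band is split.

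The conclusion assumes first US evidence in 2012-2016 and continuous treatment. The protocol does not give the number of former study patients in the US registry. For scale only, each 5% of the 1035 would be about 52 patients (0.05 × 1035 = 51.75). This is a worthwhile, inexpensive correction and does not undermine the design.

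**What to change.** 1. **9.3.2.1.** Define US duration as minimum recorded exposure. Flag a patient as possibly starting before the first record if the first ivacaftor record is positive and no earlier medications form is negative for ivacaftor, or if participation in an ivacaftor study is recorded, where that information is available. State that an earlier form counts as negative only if it could have recorded the drug.
2. **Analysis.** Keep the main duration bands. Add a sensitivity analysis of the duration-stratified results that shows flagged patients separately from the short-duration bands.
3. **9.1, Table 4, 9.3.5 and 9.9.** Say that the statement on more than 5 years rests on UK start dates, or on US records before 2012 if they exist. Reconcile it with the 2012-based US variable and with the covariate in 9.3.5. List the truncation as a limitation.

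The cost is wording, one derived flag and one sensitivity analysis. The flag will also catch some true new users who began between launch and their first visit, which is why it belongs in a sensitivity analysis and should not replace the main bands. The unflagged short-duration groups will be smaller, and the claim about maximum exposure becomes less favourable. The study-participation trigger may be of limited use, because the protocol mentions that information only on condition that it is available and Table 4 lists no such field.
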